5.2 Data and Statistical Analysis

Sample Size

The same design used in Aim 1 applies to Aim 2. We analyze the change in thrombin generation from enrollment to 2 months following initiation of study drug. We hypothesize that the anticoagulation drug will

Impact of Daily Prophylaxis Dose Anticoagulation with a Factor Xa Inhibitor (Apixaban) in Patients with Sickle Cell Disease

cause a decrease in thrombin generation from baseline to two months. From the literature the standard deviation of the D-dimer measure per patient is 500. With a total of 60 patients randomized equally to each drug sequence, and conservatively assuming no correlation between D-dimer values from baseline to 2 months on the same patient, we achieve a power of 0.863 to detect a mean D-dimer difference in the change from baseline to 2 months between the placebo and the daily prophylactic anticoagulation dose groups of 250 mg/l $\{= [(1000-750) - (1000-1000)] \text{ mg/l}\}$ for a one-sided 0.05 test.

No studies to date have evaluated the influence of anticoagulants on thrombin generation as measured by CAT, therefore sample size and expected differences are calculated based on available studies examining D-dimer.

Statistical Analysis

For our primary outcome, we will compare mean changes in thrombin generation (D-dimer, TAT and phases of CAT) for patients treated with prophylactic dose anticoagulation and placebo. Secondary outcomes will include correlation of hypercoagulable and inflammatory markers to clinical outcomes (such as pain, hospitalization, and number of acute care visits).

In addition, we expect that 50% of the patients to be hospitalized and continue their medication (placebo or drug) as assigned at randomization. For these patients, thrombin generation D-dimer measures will be collected at admission, 3 days and 5 days. Therefore, as a secondary aim, for these hospitalized patients we will analyze the difference between the placebo and drug groups in the change over time in the mean D-dimer values.

Planned Analysis of Primary Endpoint

Following the enrollment of the 60 patients, and completion of the 7 month study period for each patient, all data will be subsequently analysed with the assistance of the Duke Translational Medical Institute. [name] is our lead statistician who will continue to provide statistical support and analysis through this study.

Primary analysis of daily pain scores will be performed for patients on treatment with Apixaban and compared to patients on placebo, to determine if treatment decreases daily pain scores. In addition, we will compare changes in thrombin generation from enrollment to 2 months for patients treated with Apixaban versus placebo.

Secondary analysis will be performed to evaluate differences when patients are hospitalized and on study drug versus placebo, as well as healthcare utilization for patients treated with Apixaban.

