3.0 Study Design

This is a double blind, parallel group, placebo controlled feasibility study (see figure 1) with an enrollment target of 60 patients (30 per arm). All subjects that meet inclusion criteria as an outpatient, following a 1 month observation, will be randomized to receive an oral prophylactic dose factor Xa inhibitor (Apixaban 2.5mg po bid) or placebo for 6 months. Subjects will return for a 30 day (+/- 5 days) follow-up visit after the End of Treatment (EOT) visit. Initial randomization will occur by computerized randomization technique by the investigational drug services (IDS) at Duke University Medical Center.

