- PROs assessing fatigue, physical function, and pain impact will improve in patients administered daily prophylactic dose apixaban compared to placebo.*
- We believe that there will be a significant correlation between PROs and pain scores.*

Statistical Analysis

The primary outcome of interest is to test the effect on the mean daily pain score due to the arm by time interaction. Secondary outcome will include comparison of daily pain scores while hospitalized between treatment arms and the number of hospitalizations during each treatment period.

Impact of Daily Prophylaxis Dose Anticoagulation with a Factor Xa Inhibitor (Apixaban) in Patients with Sickle Cell Disease

[figure not shown]
All analyses will be performed using SAS version 9 or greater (SAS Institute Inc., Cary, NC). Data will be analyzed using descriptive statistics including mean and standard deviation. Comparisons are to be performed using SAS's PROC GLM with a model that accounts for all fixed and random effects in the design.

5.0 Specific Aim 2: Determine the effect of prophylactic dose anticoagulation on markers of thrombin generation during outpatient steady state as well as inpatient VOC.

As described in section 3.0, we will perform a double blind, parallel group, placebo controlled feasibility study with an enrollment target of 60 patients (30 per arm).

5.1 Study Procedures Aim 2

As described earlier (Figure 1), patients begin a 1 month observation following randomization. Patients will have blood drawn on enrollment and when they return in 1 month (+/- 5 days) to begin study drug. Subsequent blood draws performed at 2 month intervals while on study drug. Blood draws will occur between 2 and 4 hours from previous dose taken and ± 5 days regardless of hospitalization. Patients will be called monthly between in person visits to assess for AE/SAE and to reinforce the importance of medication compliance. Graded incentives may be given monthly to encourage patients to continue on study and return for follow up blood draws.

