6.1.2 Observational Period (30 days)

Via a telephone contact at 2 weeks, the investigator or designee will:

- Assess concomitant medication use
- Review pain log completion guidelines
- Assess adverse events

6.1.3 Month 1

The investigator or designee will:

- Obtain blood samples for research laboratory tests
 - Research labs include: D-dimer, thrombin-antithrombin, and calibrated automated thrombography.
- Assess concomitant medication use
- Perform Pain Score
- Dispense study drug
- Assess pain log completion compliance
- Assess adverse events

6.1.4 Month 1, 2, 3, 4, 5, 6, 7 and 8 (telephone) – 2 weeks following last clinic visit

Via a telephone contact, the investigator or designee will:

- Assess concomitant medication use
- Review pain log completion guidelines
- Assess adverse events

6.1.5 Month 2

The investigator or designee will:

- Assess concomitant medication use
- Perform Pain Score
- Dispense study drug
- Assess pain log completion compliance
- Assess adverse events
- Perform Patient Reported Outcome Computerized Questionnaire (PROMIS)

6.1.6 Month 3

The investigator or designee will:

- Obtain blood samples for research laboratory tests
 - Research labs include: D-dimer, thrombin-antithrombin, and calibrated automated thrombography.
- Assess concomitant medication use
- Perform Pain Score
- Assess study drug compliance

Impact of Daily Prophylaxis Dose Anticoagulation with a Factor Xa Inhibitor (Apixaban) in Patients with Sickle Cell Disease

- Dispense study drug
- Assess pain log completion compliance
- Assess adverse events

6.1.7 Month 4

The investigator or designee will:

- Assess concomitant medication use
- Perform Pain Score
- Assess study drug compliance
- Dispense study drug
- Assess pain log completion compliance
- Assess adverse events

6.1.8 Month 5

The investigator or designee will:

- Obtain blood samples for research laboratory tests
 - Research labs include: D-dimer, thrombin-antithrombin, and calibrated automated thrombography, IL-6, and sVCAM.
- Assess concomitant medication use
- Perform Pain Score
- Assess study drug compliance
- Dispense study drug
- Assess pain log completion compliance
- Assess adverse events

6.1.9 Month 6

The investigator or designee will:

- Assess concomitant medication use
- Perform Pain Score
- Assess study drug compliance
- Dispense study drug
- Assess pain log completion compliance
- Assess adverse events

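### The Aim 2 marker contrast stops at Month 3 and leaves the scheduled Month 5 on-drug sample out; a baseline-adjusted repeated-measures model would use both draws at little cost.

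*Combined protocol and SAP*

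**What the plan says.** Section 5.2 (Sample Size) defines the comparison: "We analyze the change in thrombin generation from enrollment to 2 months following initiation of study drug". The Planned Analysis of Primary Endpoint paragraph repeats it: "we will compare changes in thrombin generation from enrollment to 2 months for patients treated with Apixaban versus placebo". The Statistical Analysis paragraph between them lists D-dimer, TAT and the CAT phases as the primary outcome and gives no time point.

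Section 5.1 gives the sampling times: "Patients will have blood drawn on enrollment and when they return in 1 month (+/- 5 days) to begin study drug", and then "Subsequent blood draws performed at 2 month intervals while on study drug". In section 6 the on-drug draws appear at Month 3 and Month 5. For Month 5 (6.1.8) the list reads "Research labs include: D-dimer, thrombin-antithrombin, and calibrated automated thrombography, IL-6, and sVCAM". Month 7, the end of treatment, lists no draw, and the Month 8 draw is taken after treatment has ended. Months 3 and 5 are therefore the only outpatient on-drug draws listed in section 6.

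Aim 2, as worded in 5.0, concerns the effect on thrombin-generation markers in the outpatient steady state and during inpatient crisis. It fixes no month.

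**The concern.** Half of the listed on-drug outpatient marker data stand outside the primary marker comparison. A single draw of a marker with an assumed SD of 500 carries the whole on-drug side, and a patient who misses Month 3 but attends Month 5 contributes nothing. Month 5 needs no extra patient, visit or planned assay.

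The issue matters more because Aim 2 has little power to spare. On the plan's own inputs, the parallel-group comparison of change scores has power near 0.39.

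**Working it through.** **Inputs.** From the plan: 60 patients, 30 per arm (3.0); SD 500 for one D-dimer value, difference in change 250, zero correlation between baseline and 2 months, one-sided 0.05, stated power 0.863 (all 5.2). Every other correlation below is an assumption, because the documents give none for Month 5. Full attendance and an effect of 250 at both months are also assumed unless stated otherwise.

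**Formula.** SE = 500 × √(v × 2/30), where v is the per-patient variance in units of 500². Power = Φ(250/SE − 1.645), a normal approximation that ignores the small cost of estimating the covariate slope.

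**The plan's own figure.** For a change score v = 2(1 − r). At r = 0, v = 2, SE = 182.6, 250/182.6 = 1.369 and power = 0.391. The stated 0.863 does not follow from the stated parallel design. It does appear for 60 patients in a paired (crossover) comparison with difference SD 707, which would fit the wording "With a total of 60 patients randomized equally to each drug sequence". That is a separate matter.

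**Step 1: adjust for enrollment instead of subtracting it (Month 3 only).** v = 1 − r². At r = 0, v = 1, SE = 129.1 and power = 0.615. No additional sample is used.

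**Step 2: add Month 5, equal correlation r among all three draws.** For the mean of Months 3 and 5, adjusted, v = (1 + r)/2 − r². For the unadjusted change, v = 1.5(1 − r).

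| r | Change, M3 | Change, M3+M5 | Adjusted, M3 | Adjusted, M3+M5 | Adjusted variance ratio |
|---|---|---|---|---|---|
| 0 | 0.391 | 0.475 | 0.615 | 0.863 | 0.50 |
| 0.5 (assumed) | 0.615 | 0.723 | 0.723 | 0.863 | 0.67 |

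The plan's zero applies only to baseline against 2 months. If that holds but Months 3 and 5 correlate at c, the adjusted ratio is (1 + c)/2. At an assumed c = 0.5 it is 0.75, which gives SE = 129.1 × √0.75 = 111.8 and power 0.723.

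**Step 3: correlation that decays with time.** Let q be the assumed correlation per 2 months. Enrollment to Month 3 is 3 months (q^1.5), Month 3 to Month 5 is 2 months (q), and enrollment to Month 5 is 5 months (q^2.5). Adjusted v is 1 − q³ for Month 3 alone, and (1 + q)/2 − [(q^1.5 + q^2.5)/2]² for the mean of both.

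| q | Adjusted v, M3 | Adjusted v, M3+M5 | Ratio | Power, adjusted | Ratio, raw change |
|---|---|---|---|---|---|
| 0.3 | 0.973 | 0.639 | 0.66 | 0.62 to 0.78 | 0.86 |
| 0.5 | 0.875 | 0.680 | 0.78 | 0.66 to 0.76 | 0.94 |
| 0.7 | 0.657 | 0.602 | 0.92 | 0.77 to 0.80 | 1.03 |
| 0.8 | 0.488 | 0.485 | 0.99 | 0.870 to 0.872 | 1.08 |

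At q = 0.85 the adjusted ratio is 1.035, a small loss. With raw change scores, adding Month 5 already loses precision at 0.7.

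**Step 4: an effect that fades.** If the Month 5 effect is a fraction f of the Month 3 effect, averaging helps only while (1 + f)/2 exceeds the square root of the variance ratio, that is f > 2√ratio − 1. The break-even is about 0.76 at q = 0.5 and 0.92 at q = 0.7.

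**Step 5: attrition.** With 25 per arm (the 50 patients that 4.2 uses for Aim 1) and zero correlation throughout, power is 0.346 for the plan's change score, 0.549 with adjustment and 0.804 with adjustment and Month 5.

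**The case against.** The strongest reply is that the effect at 2 months on drug is a legitimate target. It is stated twice in the same terms, and the sample size is written for it. Averaging over Months 3 and 5 changes the question as well as the precision. This stands: the contrast is not an error. The documents, however, give no reason to prefer Month 3 to Month 5, and Aim 2 does not ask for that month.

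The gain also depends on a correlation the documents do not supply, and Month 5 will have at least as much dropout as Month 3. Both stand, and both limit what can be claimed.

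A reader might go further in four ways that the text does not support:

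- *Month 5 has no use at all.* It is absent from every stated contrast. However, the primary-outcome sentence gives no time point, and the secondary correlations of markers with clinical outcomes could draw on Month 5 values.
- *The two on-drug samples are assayed together.* Section 5.1 says only that plasma is stored so that batch testing is possible.
- *Averaging is worth a fixed 25% of the variance, or 20 extra patients.* That holds for raw change under equal correlation, and not when correlation decays.
- *Adding Month 5 restores the stated 0.863.* The adjusted figure of 0.863 matches by arithmetic coincidence, under a different analysis. Raw-change averaging reaches only 0.475 at zero correlation.

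Finally, 4.2 names PROC GLM. Used with a REPEATED statement, it drops any patient who lacks either draw, so adding Month 5 that way could make the missed-visit problem worse. The fix has to name the model.

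**Conclusion.** The point holds as an efficiency improvement. The marker contrast is valid, but it leaves out a scheduled on-drug draw that the aim gives no reason to exclude.

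The more dependable part is the enrollment adjustment, which alone takes power from 0.39 to 0.615 at the plan's zero correlation. The further gain from Month 5 runs from substantial (variance ratio 0.50 with no correlation, 0.66 at an assumed 0.3 per 2 months) to none (about 1.0 at 0.8). It requires an effect and attendance that persist to Month 5. The discrepancy between the stated 0.863 and about 0.39 is a larger, separate problem that this change does not settle.

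**What to change.** In 5.2 and the Planned Analysis paragraph, specify that Month 3 and Month 5 marker values are analysed in a likelihood-based mixed model for repeated measures. Include arm, visit, arm-by-visit and the enrollment value as covariate. Make the arm difference averaged over Months 3 and 5 the primary marker contrast, and report the Month 3 difference from the same model as a supporting estimate. State that PROC GLM with REPEATED will not be used for this analysis, so that a patient with one on-drug draw still contributes.

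The cost is wording, to be settled before unblinding, with no change to visits or sampling. The price is a changed target: the average effect over 2 to 4 months on drug, which is diluted if the effect or adherence falls by Month 5. The supporting Month 3 estimate keeps the present question answerable.

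### Aim 2 compares an unadjusted change from the single enrollment draw; adjusting for both pre-dose draws would be more precise at almost no cost, and the stated power of 0.863 needs restating

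*Combined protocol and SAP*

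**What the plan says.** Section 5.2 (Sample Size) defines the Aim 2 comparison: "We analyze the change in thrombin generation from enrollment to 2 months following initiation of study drug". Under Planned Analysis of Primary Endpoint the same section repeats it: "we will compare changes in thrombin generation from enrollment to 2 months for patients treated with Apixaban versus placebo". Drug starts at the Month 1 visit and no blood is scheduled at Month 2, so the 2-month value is the Month 3 draw (section 6.1.6).

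Section 5.1 schedules two draws before any drug is taken: "Patients will have blood drawn on enrollment and when they return in 1 month (+/- 5 days) to begin study drug". Section 6.1.3 confirms that the Month 1 visit, where study drug is first dispensed, includes the same coagulation markers: "Research labs include: D-dimer, thrombin-antithrombin, and calibrated automated thrombography".

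The sample size takes its measure of spread from published work: "From the literature the standard deviation of the D-dimer measure per patient is 500". The power claim reads "we achieve a power of 0.863 to detect a mean D-dimer difference in the change from baseline to 2 months", and the test level is given as "for a one-sided 0.05 test". On how strongly a patient's two values are related, the calculation proceeds by "conservatively assuming no correlation between D-dimer values from baseline to 2 months on the same patient". The difference is 250, from 1000 to 750 on drug against 1000 throughout on placebo. Sections 3.0 and 5.0 give 60 patients, 30 per arm, in a parallel design.

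The analysis paragraph for Aim 1 (section 4.2) names PROC GLM with the design's fixed and random effects. Section 5.2 says the Aim 1 design carries over. Neither section names a baseline covariate.

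**The concern.** Two features of the stated contrast give up precision.

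First, it is a raw change score. Subtracting a baseline helps only when the baseline predicts the later value well. If the two are uncorrelated, as the plan assumes, subtraction adds the baseline's noise and doubles the variance. ANCOVA estimates how much of the baseline to subtract, so in large samples it is never less efficient.

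Second, the contrast uses one of two available pre-dose values, and the one further from treatment. A mean of two values is a less noisy baseline.

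The marker comparison is one of the trial's two aims and has only 30 patients per arm, so precision obtainable from samples already scheduled is worth having. The validity of the comparison is not at stake.

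**Working it through.** **Inputs.** 30 per arm (sections 3.0, 5.0); SD 500, difference 250, one-sided 0.05, correlation r = 0 (section 5.2). The documents give no other correlation, so every figure with r > 0 is an assumption shown as a range.

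**The plan's own figure first.** The SD of a change is 500 × √(2(1−r)), which is 707 at r = 0. With 30 per arm the standardised difference is 250 / (707 × √(2/30)) = 1.369. By the normal approximation, power = Φ(1.369 − 1.645) = 0.391; by the noncentral t with 58 df it is 0.385. The plan states 0.863. That value is reproduced with 60 per arm and SD 500: 250 / (500 × √(2/60)) = 2.739, and Φ(2.739 − 1.645) = 0.863. A 60-patient crossover with SD 500 per value and zero correlation gives the same number, and the Aim 2 text does speak of allocation to drug sequences. Neither matches 30 per arm with an uncorrelated change score.

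**Variance under each analysis**, in units of 500², with equal correlation r among the enrollment, Month 1 and Month 3 draws:

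- change from enrollment: 2(1−r)
- change from the mean of both pre-dose draws: 1.5(1−r)
- ANCOVA on one draw: 1 − r²
- ANCOVA on the mean of both: 1 − 2r²/(1+r)

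Example at r = 0.5: 1.000, 0.750, 0.750 and 0.667, so SDs of 500, 433, 433 and 408.

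**Power**, 30 per arm, noncentral t with 58 df (ANCOVA strictly has 57, a negligible difference):

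| r | Change from enrollment | Change from mean of two | ANCOVA, one draw | ANCOVA, mean of two |
|---|---|---|---|---|
| 0 (plan) | 0.385 | 0.467 | 0.606 | 0.606 |
| 0.3 | 0.489 | 0.588 | 0.641 | 0.662 |
| 0.5 | 0.606 | 0.714 | 0.714 | 0.758 |
| 0.7 | 0.796 | 0.886 | 0.850 | 0.902 |
| 0.8 | 0.916 | 0.968 | 0.939 | 0.972 |

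**Separating the two causes.**

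- At r = 0 the whole gain, 0.385 to 0.606, comes from dropping the change score; Month 1 adds nothing.
- At r = 0.5, dropping the change score gives 0.714 − 0.606 = 0.108, and Month 1 then adds 0.758 − 0.714 = 0.044.
- At r = 0.7 the two parts are 0.054 and 0.052.
- If a change score is kept, averaging the two draws cuts its variance by 25% at every r. That is worth 0.082 at r = 0, 0.108 at 0.5 and 0.052 at 0.8.

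**Sensitivity to unequal correlation.** Suppose correlation decays by a factor m per month, so that it is m³ from enrollment to Month 3, m² from Month 1 to Month 3, and m between the two pre-dose draws. The residual variance of ANCOVA on the mean is then 1 − [(m³+m²)/2]² / [(1+m)/2]. Power for the change score, ANCOVA on enrollment alone and ANCOVA on the mean is 0.421/0.612/0.624 at m = 0.5, 0.615/0.720/0.777 at m = 0.8 and 0.830/0.875/0.930 at m = 0.9. The Month 1 draw then adds about 1 to 6 points under ANCOVA.

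**Can the better model reach 0.863?** At r = 0.65 its variance is 1 − 2(0.4225)/1.65 = 0.488 and its power is 0.863. Below that correlation it falls short.

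**The case against.** The strongest reply is that this is a preference about efficiency. A between-arm comparison of change from a pre-dose value is unbiased under randomisation, and the study is described as a feasibility study. That stands: no error of inference is shown.

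A second reply is that the model is under-specified rather than shown to exclude Month 1. Section 5.2 carries over the Aim 1 design, the PROC GLM sentence is broad, and the word baseline is not defined. That is fair, but the only contrast written down starts at enrollment, it is stated twice, and no covariate is named. If another model is intended, it should be stated.

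Three stronger readings are tempting and should be resisted:

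- A reader might infer that omitting the Month 1 draw by itself costs a large share of the power. At the plan's zero correlation it costs nothing under ANCOVA and 8 points with a change score. Over r = 0 to 0.8 the ranges are about 0 to 5 and about 5 to 11 points.
- A reader might blame the choice of baseline for the gap between about 0.39 and 0.863. That gap arises because the stated figure does not follow from its inputs.
- A reader might expect the new model to restore 0.863. At r = 0 it gives 0.606.

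The combined gain also shrinks as correlation rises: at r = 0.8 it is 0.972 − 0.916, about 6 points.

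**Conclusion.** The point holds as an efficiency improvement. The planned contrast is valid, but it leaves precision unused. Replacing it with ANCOVA on both pre-dose draws raises power by 22 points at r = 0, 15 at r = 0.5, 11 at r = 0.7 and 6 at r = 0.8. At low correlation nearly all of this comes from replacing the change score; by r = 0.7 the adjustment and the Month 1 draw contribute about equally.

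Separately, the Aim 2 power of 0.863 is not supported by the plan's inputs. The planned analysis gives about 0.39 at zero correlation.

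These sizes assume SD 500 at every draw, complete data on 30 per arm, and the assumed correlation patterns. The figures at r = 0 need no correlation beyond the plan's own, extended to the Month 1 draw.

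**What to change.** In section 5.2, make the primary Aim 2 analysis an ANCOVA of the Month 3 value with arm as factor and the mean of the enrollment and Month 1 pre-dose values as covariate. Where one pre-dose value is missing, use the other. Apply the same model to TAT and each CAT parameter, and define baseline explicitly as this mean.

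Restate the Aim 2 power for 30 per arm under that model over a range of correlations, including zero, and remove the crossover wording about sequences.

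The cost is wording and a short recalculation, settled before unblinding. Both draws, with these assays, are already scheduled. The restated power may be well below 0.863, and the plan should then say so.

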principal investigator. Pain scores during hospitalization and for the subsequent 1 week will be recorded and used for secondary analysis of daily pain scores during crisis.

Patients who during the course of the study have laboratory findings which reveal creatinine ≥ 1.5 mg/dL AND weight ≤ 60 kg; platelets $< 100 \times 10^9/L$; or develop AST or ALT > 3 times normal, will have study drug stopped and will be terminated from the study.

Patients on hydroxyurea will be included in the study and sub-analysis will be performed to control for potential differences. All patients despite treatment with hydroxyurea will need to meet inclusion criteria of having clinically significant pain which requires > 2 acute care visits.

4.2 Data and Statistical Analysis Aim 1

We power the study to test whether there is a significantly larger reduction in pain after administration of a daily prophylactic anticoagulation dose as compared to administration of a placebo. A total of 60 patients will be randomly assigned to each drug arm. The primary endpoint is the mean pain score per patient over each of four time periods. The design has two sources of variation: the variation between the patients receiving the same drug and the variation due to the interaction of time by the patients within drug arm. It is of interest to test whether the change in the pain score over the four time periods differs between the prophylactic anticoagulation dose arm and the placebo arm. From the literature the standard deviation of the mean pain score per patient is 1.5. Assume the true mean pain scores over the four time periods for the placebo and prophylactic anticoagulation dose arms are 3.9, 3.9, 3.9, 3.9 and 3.9, 3.12, 3.12, 3.12, respectively. Then, a total of 60 patients randomized equally to each drug arm will detect the difference in the change between the two arms in the mean pain scores over time, as specified by the preceding mean pain scores, with a power of at least 0.836 for a one-sided 0.05 test. Anticipating that 20% (10 patients) may have incomplete data (less than 75% of daily pain scores recorded or missing more than one dose of study drug per week), may be lost to follow up, or may drop out; we have also found a power of at least 78.4% for 50 patients.

We expect two positive effects from prophylactic doses of apixaban on the patient reported outcomes:

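### The Aim 2 D-dimer power is stated only for 60 complete sample pairs, although Section 4.2 plans for losses in the same patients

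*Combined protocol and SAP*

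**What the plan says.** Section 5.2 (Sample Size) ties the two aims together: "The same design used in Aim 1 applies to Aim 2". The comparison is the change in D-dimer from enrollment to 2 months after study drug starts. Its inputs are a per-measurement SD ("From the literature the standard deviation of the D-dimer measure per patient is 500"), zero within-patient correlation, a between-arm difference in change of 250 mg/l, and a test described as "for a one-sided 0.05 test". The result is given for 60 patients only. The power sentence opens "With a total of 60 patients randomized equally to each drug sequence, and conservatively assuming no correlation between D-dimer values from baseline to 2 months" and goes on to the result: "we achieve a power of 0.863 to detect a mean D-dimer difference in the change from baseline to 2 months".

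Section 4.2 treats the same patients differently for Aim 1. It anticipates that 20%, glossed as 10 patients, will have fewer than 75% of daily pain scores, will miss more than one dose a week, or "may be lost to follow up, or may drop out; we have also found a power of at least 78.4% for 50 patients".

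Section 5.2 has no matching sentence. It gives no loss rate for blood samples, no power at a smaller number and no statement that losses by 2 months will be negligible.

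**The concern.** A change score needs both samples. The first is drawn at the screening and randomization visit (Section 6.1). The second is the draw two months into treatment, at Month 3 (Section 6.1.6), about three months later. A patient who leaves in between drops out of the comparison, and the plan describes no imputation. Section 4.1 also ends participation for certain laboratory findings, and loss to follow-up and drop-out are not specific to the pain endpoint.

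So one cohort is planned with losses for one aim and without them for the other. Section 5.2 calls thrombin generation the primary outcome of Aim 2, and the enrollment-to-2-month comparison appears again under the planned analysis of the primary endpoint. A reader will take the printed power as the chance of detecting the D-dimer difference in the trial as it is expected to run. If the figure were corrected for variance but still quoted only for 60 pairs, it would still make no allowance for missing pairs.

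**Working it through.** **Inputs.** Difference in change 250, SD of a single measurement 500, correlation 0 and one-sided alpha 0.05 (Section 5.2); 30 per arm, parallel groups (Sections 3.0 and 5.0); 20% or 10 patients lost, 50 remaining (Section 4.2).

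**Formulas.** SD of change = 500 × √(2(1 − ρ)). With ρ = 0 this is 500 × √2 = 707.1. With n per arm, the noncentrality is 250 / (SD of change × √(2/n)). The normal approximation to power is Φ(noncentrality − 1.645). The t-test version uses the noncentral t distribution with 2n − 2 degrees of freedom.

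**The plan's own figure.**

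- On the stated inputs, 707.1 × √(2/30) = 182.6 and 250/182.6 = 1.369. Power is Φ(1.369 − 1.645) = 0.391, or 0.385 by the t test. The printed 0.863 is not reproduced.
- It is reproduced with 60 per arm and an SD of change of 500: 500 × √(2/60) = 91.3, 250/91.3 = 2.739, and Φ(2.739 − 1.645) = 0.863 (0.859 by the t test). Equivalently, it follows from 60 within-patient differences with SD 707.1, a crossover-type formula that would fit the plan's reference to drug sequences.
- At 30 per arm, 0.863 would need an SD of change of about 354, that is ρ = 0.75, against the stated zero.

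This mismatch is a separate and larger problem. The effect of losses is therefore shown on three bases:

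- (a) the stated inputs;
- (b) 30 per arm with SD of change 500 (ρ = 0.5, an assumption not in the plan);
- (c) the basis behind 0.863, with 60 per arm reduced in the same proportion.

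**Power by noncentral t, with points lost in brackets.**

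| Patients with both samples | Loss | (a) | (b) | (c) |
|---|---|---|---|---|
| 60 | none | 0.385 | 0.606 | 0.859 |
| 55 | 8% (assumed) | 0.363 (2.2) | 0.574 (3.2) | 0.832 (2.8) |
| 54 | 10% (assumed) | 0.358 (2.7) | 0.567 (3.9) | 0.826 (3.4) |
| 50 | 10 of 60 = 16.7% | 0.340 (4.5) | 0.539 (6.7) | 0.799 (6.1) |
| 48 | 20% | 0.331 (5.5) | 0.525 (8.1) | 0.784 (7.5) |

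Points lost are taken from unrounded powers. The normal approximation gives the same pattern: at 48 patients the losses are 5.4, 8.0 and 7.3 points.

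**The loss figure itself.** 20% of 60 is 12, leaving 48. Ten of 60 is 16.7%, leaving 50. Section 4.2 uses both without reconciling them, which is why both rows are needed.

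**The case against.** The strongest reply is that the 20% is not a rate of missing D-dimer samples. It mixes sparse pain diaries and missed doses with loss to follow-up and drop-out, and the shares are not given. A patient with a poor diary can still give both blood samples. The Aim 2 comparison closes two months into a six-month treatment period, and Section 5.1 keeps the draw schedule during hospital stays and allows incentives for returning to give blood. All of this stands, and it makes the 20% an upper-end assumption.

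A reader might infer that the D-dimer power is overstated by a fixed 5 to 8 points whatever the variance, or that the plan itself expects only 48 to 50 pairs. The documents support neither. They state no expected number of pairs. At the plan's own 50 patients the loss on the stated inputs is 4.5 points, and the upper end of the range comes only from bases (b) and (c), which are not the plan's stated inputs.

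It can also be said that Section 5.2 openly quotes its power for 60, so this is an omission and not a miscalculation, and that the study calls itself a feasibility study. That is fair, and it limits the weight of the point. It does not remove the inconsistency: nothing in the documents supports zero loss of pairs, and the loss and termination provisions apply to the same patients.

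**Conclusion.** The point holds in a conditional form. Section 5.2 gives its D-dimer power only for 60 complete pairs, while Section 4.2 plans for losses in the same cohort and restates the Aim 1 power accordingly. If the Section 4.2 loss carried over in full, the fall would be about 4.5 to 5.5 points on the stated inputs and about 6 to 8 points on the alternative bases. At an assumed 8-10% loss it would be about 2 to 4 points. The direction is the same on every basis; the size depends on a loss rate that the plan does not give.

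Attrition does not explain why 0.863 fails to follow from the stated inputs. That gap, 0.863 against about 0.39, is far larger, and the loss allowance is secondary to it. The two are best corrected together, because a restated figure of about 0.39 would still assume that every pair is obtained.

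**What to change.** When Section 5.2 is restated on the parallel-design variance (about 0.39 at 60 patients, or 0.385 by t test), add:

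- an expected loss rate for paired D-dimer samples by 2 months on drug, with its reason;
- the power at the resulting number of pairs, next to the figure for 60. With the Section 4.2 loss this is about 0.33 to 0.34 on the stated inputs. If the sponsor expects fewer losses by Month 3, it should state that lower rate and give the power at it.

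In Section 4.2, reconcile 20% with 10 patients: either 12 lost and 48 remaining, or 10 lost, 16.7% and 50 remaining.

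The cost is a sentence or two and a re-run of the power calculation. No change to enrollment is proposed. The downside for the sponsor is a less favourable stated power.
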